5. TREATMENT PLAN

5.1 Agent Administration

Patients with surgically incurable stage III or IV melanoma and tissue amenable to serial biopsy will undergo pretreatment tumor biopsy and receive a 3-month course of INCIB024360 administered as a twice daily continuous dosing oral regimen. The

MELITAC 12.1 vaccine has 3 components: 12-MP peptides, Peptide-tet, and Montanide ISA-51 VG vaccine adjuvant, which will be prepared together as an emulsion for administration. Three (3) mL of emulsion will be prepared. Two (2) mL of this emulsion will be administered, with 1 mL at each of 2 vaccine sites. At each site, half of each dose (0.5 mL) will be injected subcutaneously and half (0.5 mL) will be injected intradermally. The remaining 1 mL of the prepared emulsion will be discarded.

On day 21, a week 3 tumor biopsy will be collected and the effects of inhibitor alone on the tumor microenvironment will be evaluated by comparing the pretreatment tumor biopsy to the day 21 tumor biopsy, assessing changes in IHC and gene signatures.

Note: The biopsy on day 21 is mandatory. For patients with only one or two tumors approachable for biopsy, available tumor blocks from prior biopsies can serve as the pretreatment sample.

Also on day 21, a vaccination regimen with MELITAC 12.1 multipeptide vaccine will begin, with vaccines administered on days 21, 28, 35, 56, 77, and 98 (Weeks 3, 4, 5, 8, 11, and 14). MELITAC 12.1, will be administered intradermally/subcutaneously at a fixed dose of 2.0 ml for 6 vaccinations. On day 42, tumor will be biopsied and the effect of continued INCB024360 plus vaccine on the tumor microenvironment will be evaluated by comparing the week 3 tumor biopsy to the week 6 tumor biopsy, assessing changes in IHC and gene signatures.

Patients will receive 3 weeks of INCB024360, followed by continued INCB024360 plus 6 vaccinations with MELITAC 12.1. Patients who have disease progression while receiving anti-PD1 or anti-PDL-1 antibody treatment will be allowed to enroll and receive INCB024360 within 2-6 weeks of last antibody treatment administration. Patients enrolled within the 6 week window will be enrolled in Cohort B and administered INCB024360 orally at a dose of 100 mg twice daily continuously up to day 98 (3 months) plus vaccines. Patients who enroll in the study after confirmed disease progression on anti-PD1/PDL-1 after 6 weeks of receiving the last dose of antibody will be enrolled in Cohort A and receive 300 mg BID of INCB024360 plus vaccines.

Patients that show response at 3 months will be considered for additional INCB024360.

As a lead-in to ensure safety and tolerability of the combination of INCB024360 and MELITAC 12.1, the first 3 patients enrolled in the study will be at the dose of 300 mg bid staggering each patient's enrollment by at least 2 weeks so that the first patient will receive 2 doses of the vaccine in combination with INCB024360 before the second patient starts the combination of agents. Enrollment will be halted after the first 3 patients are enrolled to allow for observation of any toxicity before opening further enrollment. The next nine patients will receive either 300 mg bid of INCB024360 or 100 mg bid ([Table 5.1](#)). For patient safety, if a Dose Limiting Toxicity (DLT) occurs in the first three patients treated at the 300 mg BID dose level of INCB024360 + MELITAC 12.1 vaccine, the subsequent 9 patients will be treated with the dose of either 300 mg BID or 100 mg of INCB024360 + MELITAC 12.1. If two DLTs occur in the first 6 patients treated at the

300 mg dose of INCB024360 + MELITAC 12.1 the study will be stopped.

Treatment will be administered on an outpatient basis. Reported AEs and potential risks are described in [Section 7](#). Appropriate dose modifications are described in [Section 6](#). No investigational or commercial agents or therapies other than those described below may be administered with the intent to treat the patient's malignancy. The patient will be requested to maintain a medication diary of each dose of medication. The medication diary will be returned to clinic staff at the end of each course.

[Table 5.1. Agent Administration and Timing of Assessments](#)

Cohort	INCB024360 Dosing	MELITAC 12.1 Dosing	Blood draws	Tumor biopsies including FNA
A Pts.enrolled >6 wks after failing anti- PD-1/PDL-1	300 mg po bid continuous for 98 days (3 months)	Intradermal/subcutaneous Days 21, 28, 35, 56, 77, 98 (Weeks 3, 4, 5, 8, 11, and 14)	Pretreatment day 0 and on days 21, 42, 98, and 112	Days 0, 21, 42, and (optional day 112) and (optional when coming off study including for progression)
B Pts.enrolled 2-6 wks after failing anti- PD-1/PDL-1	100 mg po bid continuous for 98 days (3 months)	Intradermal/subcutaneous Days 21, 28, 35, 56, 77, 98 (Weeks 3, 4, 5, 8, 11, and 14)	Pretreatment day 0 and on days 21, 42, 98, and 112	Days 0, 21, 42, and (optional day 112) and (optional when coming off study including for progression)

Abbreviations: bid, twice per day; FNA, fine-needle aspiration; po, orally; pre-tx, pretreatment; SC, subcutaneous

Enrollment will be staggered so that only 3 patients will initially be treated at the 300-mg bid dose in order to observe their response to the INCB024360-MELITAC 12.1 combination. After the first patient is started on INCB024360, treatment will proceed for 2 weeks before the second patient is started on INCB024360 monotherapy. Before the second patient starts the combination of INCB024360 and MELITAC 12, the first patient will have already received the second vaccination of MELITAC 12.1 in combination with INCB024360 and observed for any toxicity. The third patient will start INCB024360 monotherapy 2 weeks after patient number 2 has received the combination of INCB024360 and MELITAC 12.1 and been observed for toxicities. After the first 3 patients are treated at the 300-mg bid dose of INCB024360 in combination with the MELITAC 12.1 and found to tolerate the combination well, the dose of INCB024360 will be 300 mg BID for subsequent patients. Those patients treated with anti-PD-1/PDL1 antibody who have failed therapy and enrolled in the study 6 weeks or longer after progression of disease will be enrolled in Cohort A and receive 300 mg BID of INCB024360. Patients who fail anti-PD-1/PDL-1 therapy and enroll within 2-6 weeks of progression of disease will receive 100 mg BID in Cohort B. All other patients enrolled in the study will receive INCB024360 300 mg BID.

A total of 12 patients will be enrolled in the study. Assignment to Cohort A or B is for dose assignment only.

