
The study protocol and all related forms and documents must be downloaded from the protocol-specific Web page of the CTSU Member Web site located at https://www.ctsu.org. Sites must use the current form version and adhere to the instructions and submission schedule outlined in the protocol.
 
CITN sites should follow procedures outlined in the protocol for Site registration, Patient Enrollment, Adverse Event Reporting, Data Submission (including ancillary studies), and Drug Procurement.
		

For questions unrelated to patient eligibility, treatment, or data submission contact the CTSU Help Desk by phone or e-mail: CTSU General Information Line – [name], or [contact]. All calls and correspondence will be triaged to the appropriate CTSU representative.
		

For detailed information on the regulatory and monitoring procedures for CTSU sites please review the CTSU Regulatory and Monitoring Procedures policy located on the CTSU members' website https://www.ctsu.org
		

The CTSU Web site is located at https://www.ctsu.org
		

SCHEMA

Cohort	INCB024360 Dosing	MELITAC 12.1 Dosing	Blood draws	Tumor biopsies including FNA
A Pts.enrolled >6 wks after failing anti-PD-1/PDL-1	300 mg po bid continuous for 98 days (3 months)	Intradermal/subcutaneous Days 21, 28, 35, 56, 77, 98 (Weeks 3, 4, 5, 8, 11, and 14)	Pretreatment day 0 and on days 21, 42, 98, and 112	Days 0, 21, 42, and (optional day 112) and (optional when coming off study including for progression)
B Pts.enrolled 2-6 wks after failing anti-PD-1/PDL-1	100 mg po bid continuous for 98 days (3 months)	Intradermal/subcutaneous Days 21, 28, 35, 56, 77, 98 (Weeks 3, 4, 5, 8, 11, and 14)	Pretreatment day 0 and on days 21, 42, 98, and 112	Days 0, 21, 42, and (optional day 112) and (optional when coming off study including for progression)
All other pts.	300 mg po bid	Intradermal/subcutaneous Days 21, 28, 35, 56, 77, 98 (Weeks 3, 4, 5, 8, 11, and 14)	Pretreatment day 0 and on days 21, 42, 98, and 112	Days 0, 21, 42, and (optional day 112) and (optional when coming off study including for progression)

Abbreviations: bid, twice per day; FNA, fine-needle aspiration; po, orally; pre-tx, pretreatment; SC, subcutaneous
 All other patients enrolled who have not been treated with anti-PD1/PDL-1 will receive 300 mg BID INCB024360

TABLE OF CONTENTS

SCHEMA	4
1. OBJECTIVES	7
1.1 Primary Objectives.....	7
1.2 Secondary Objectives.....	7
2. BACKGROUND	8
2.1 Study Disease(s).....	8

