Plasma levels of INC024360 and plasma levels of Kyn were measured in serial samples. Steady-state linear pharmacokinetics were obtained on or before day 8, and appreciable drug accumulation with increases in mean area under the curve (AUC) by 30% between analysis on day 1 and 15 was evident. The half-life was 2.3–4 hours. Pharmacodynamic correlates suggest that significant target inhibition was achieved at bid doses \geq 300 mg bid, resulting in steady-state exposures that exceeded the IC₉₀. As a pharmacodynamic effect, blood samples for tryptophan and kynurene levels show significant target inhibition with doses of 50 mg bid or greater. In patients showing elevations at baseline, \geq 300 mg bid doses normalize kynurene levels. IHC staining of 11 patients demonstrated that IDO1 tumor expression could be observed in tumor cells, infiltrating inflammatory cells, or both, in 10 out of 11 samples, and CD3+ T cells and Foxp3+ Tregs were present in all examined samples. Based on the tolerability and these pharmacokinetic and pharmacodynamic observations, a dose of 600 mg bid has been determined as the recommended Phase-II dose as monotherapy.

In recent preliminary results from a Phase 1/2 study of INC024360 combined with ipilimumab in patients with advanced melanoma data showed that in immunotherapy-naïve patients given 25 mg BID or 50 mg BID, 42% of patients demonstrated an objective response and 75% of patients demonstrated disease control by irRC.

[\[Gibney; Hamid 2014\]](#) It is therefore proposed that reducing the dose of INC024360 from 600 mg BID to 300 mg BID in all patients may help prevent adverse events and dose limiting toxicities without limiting biological effect.

In unpublished preliminary data from Incyte, kynurene concentrations and the Kyn/Trp ratio were higher in the serum of most patients compared to controls and decreased to levels below the median for normal, after treatment with inhibitor when treated with doses that exceeded the IC₉₀ (i.e., $>$ 300 mg bid [N=19 patients]) (Table 2.4).

Table 2.4. Changes in Kynurene Concentrations and Kyn/Trp Ratios

Serum Variables	Control Patients median	Cancer Patients median (range)	Post-inhibitor median (range)
All patients (N=19)			
Kynurene, μ M	2.0	2.1 (1.3–4.2)	0.97 (0.5–1.7)
Kyn/Trp ratio, nmol/ μ mol	29.9	37.4 (17.8–68.9)	18.3 (N/A)
Select patients*			
Kynurene, μ M	2.0	2.7 (2.1–4.2)	1.1 (0.5–1.7)
Kyn/Trp ratio, nmol/ μ mol	29.9	42.0 (34–69)	18.6 (8–43)

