10. STUDY CALENDAR

All baseline evaluations are to be conducted within 1 week before start of protocol therapy. Scans and x-rays must be done \leq 4 weeks before the start of therapy. In the event that the patient's condition is deteriorating, laboratory evaluations should be repeated within 48 hours before initiating the next cycle of therapy.

	Pre-Study -30 day	Pre-Study -7 day	Wk 0 Day 0	Wk 1 Day 7 +/- 2 d	Wk 2 Day 14 +/- 2d	Wk 3 Day 21 +/- 2d	Wk 4 Day 28 +/- 2d	Wk 5 Day 35 +/- 2d	Wk 6 Day 42 +/- 2d	Wk 8 Day 56 +/- 2d	Wk 11 Day 77 +/- 2d	Wk 14 Day 98 +/- 2d	Wk 16 Day 112 +/- 2d	Repeat ^b Cycles Wks ^c +/-2d	10 Wk Post-Tx F/U ^d F/U +/-14d	36 Wk Post-Tx FU F/U +/-30d	Off Study
INCB024360 daily			X	X	X	X	X	X	X	X	X	X	X	→	X		
MELITAC 12.1 vaccine**						X	X	X		X	X	X					
Informed consent	X																
Demographics	X																
Medical history	X																
Concomitant medication		X	X	X	X	X	X	X	X	X	X	X	X	X	X	X	X
Physical exam		X	X			X		X		X	X	X	X	X	X	X	X
Vital signs		X	X	X	X	X	X	X	X	X	X	X	X	X	X	X	X
Height		X													X		
Weight		X	X	X	X	X	X	X	X	X	X	X	X	X	X	X	X
Performance status		X	X	X	X	X	X	X	X	X	X	X	X	X	X	X	X
Tumor Biopsy ^{1,2*}			X ^a			X			X ³				X ³				X ¹
FNA ^{4,5}			X ^a			X			X				X ³				X ¹
CBC w/diff, plts (local lab)		X	X	X	X	X	X	X	X	X	X	X	X	X	X	X	X
Serum chemistry ⁶ (local lab)		X	X	X	X	X	X	X	X	X	X	X	X	X	X	X	X
B-HCG ⁷ (local lab)			X ⁷														
PBMC ⁵ and T-cell subsets			X			X			X			X	X ⁸				
IFN-gamma ELISpot***			X			X			X			X	X				
Confirmatory Tetramer staining			X			X			X			X					

	Pre-Study -30 day	Pre-Study -7 day	Wk 0 Day 0	Wk 1 Day 7 +/- 2 d	Wk 2 Day 14 +/- 2d	Wk 3 Day 21 +/- 2d	Wk 4 Day 28 +/- 2d	Wk 5 Day 35 +/- 2d	Wk 6 Day 42 +/- 2d	Wk 8 Day 56 +/- 2d	Wk 11 Day 77 +/- 2d	Wk 14 Day 98 +/- 2d	Wk 16 Day 112 +/- 2d	Repeat ^b Cycles Wks ^c +/-2d	10 Wk Post-Tx F/U [‡] F/U +/-14d	36 Wk Post-Tx FU F/U +/-30d	Off Study
Kyn/Trp ratio			X			X			X					X*			
RNA Cell Pellet for gene expression analysis			X			X			X					X			
Serum Cytokines			X			X			X					X			
INCB024360 level						X			X					X			
Circulating tumor cells			X											X			
PBMC storage***			X			X			X					X ⁸	X		
Serum storage			X			X			X					X ⁸			
EKG (pre-study and as indicated)	X																
Adverse event evaluation	X	X	X	X	X	X	X	X	X	X	X	X	X		X	X	X

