Therapeutic response will be assessed by serial scans and measures of circulating tumor cells. Overall clinical response rate and tumor progression will be assessed by evaluating nonbiopsied lesions if present, using standard methods (RECIST and irRC), including physical exam and CT scans performed before therapy, at weeks 8, 16, 26 and every 3 months through 1 year according to standard practice. If a clinical response is seen at week 8 a confirmatory scan is to be repeated at least 4 weeks later (week 12), therefore obtaining the week 16 scan may be delayed an additional 4 weeks and repeated at week 20. After week 26 scans are to be done every 12 weeks in patients without progression. Both systems will be used for reporting response. Patients may be managed in accordance with irRC guidelines as published by Wolchok [[Wolchok 2009](#)]. The irRC criteria allow for reporting as "response" patients that respond after a period of progression. The irRC criteria accordingly do not demand immediate cessation of experimental therapy with the first sign of progression.

In addition, the safety and tolerability of INCB024360 with MELITAC 12.1 will be assessed in this study utilizing the National Cancer Institute Common Terminology Criteria for Adverse Events v4.0 (NCI CTCAE v4.0).

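### The treatment text ends INCB024360 at day 98, but the Study Calendar marks daily dosing through week 16 (day 112), so it is undefined whether week-16 samples from patients given cycle 1 only are on or off drug

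*Combined protocol and SAP*

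**What the plan says.** **Text and tables.** Section 5.1 describes a three-month course for all patients, "administered as a twice daily continuous dosing oral regimen". For Cohort B it adds "twice daily continuously up to day 98 (3 months) plus vaccines"; the matching Cohort A sentence gives no duration. Table 5.1 has "300 mg po bid continuous for 98 days (3 months") for Cohort A and the same 98 days for Cohort B. The Schema repeats this, with "100 mg po bid continuous for 98 days (3 months") for Cohort B, but its row for all other patients gives a dose and no duration. Section 5.4 names no last day for the first course. It allows up to three additional cycles after consultation, and Section 5.1 says that responders at three months will be considered for more drug.

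**Calendar.** In Section 10 the row "INCB024360 daily" is marked at each visit from week 0 through the column "Wk 16 Day 112 +/- 2d", followed by an arrow into the repeat-cycles column. Patients approved for further cycles have that separate column and their own footnote. No footnote qualifies the week-16 mark.

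**Week-16 sampling.** Sections 5.4, 9.2.3, 9.2.4 and 11 place week 16 two weeks after the last vaccine. None says whether INCB024360 is still being taken then.

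**The concern.** Two operative parts of the protocol give different last dosing days, and a site cannot follow both. The difference falls exactly on the interval before the week-16 visit.

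That visit matters because Section 9.2.4 draws the week-14 blood just before the last vaccine. Week 16 is therefore the only scheduled cycle-1 immune sample taken after all six vaccinations, and it is also when the optional fourth biopsy is done. If the drug is still being taken, a week-16 ELISpot or T-cell subset result describes INCB024360 plus the full vaccine series. If it stopped at day 98, the same result describes the full series after two weeks of drug withdrawal. Section 11 compares vaccine responses with published experience without INCB024360, so the reader needs to know which state was measured. With 12 patients, a few samples in the other state could change a descriptive summary.

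**Working it through.** The plan has no figure to reproduce here. The check is a reading of the calendar followed by day arithmetic.

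**1. Is the week-16 mark real, or a product of PDF extraction?** The calendar has 11 visit columns from week 0 on: weeks 0, 1, 2, 3, 4, 5, 6, 8, 11, 14 and 16. The INCB024360 row has 11 consecutive marks starting at week 0, so the eleventh is week 16. Two rows with a known schedule test the alignment:
- The vaccine row falls on weeks 3, 4, 5, 8, 11 and 14, as in Section 5.1.
- The biopsy row falls on weeks 0, 3, 6, 16 and off study, as in Table 5.1.

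Moving the INCB024360 row one column left would put dosing at the day −7 screening visit. The reading is sound up to week 16. To the right of that column it is not: after the arrow there is a further mark under the 10-week post-treatment visit, and some rows on the second page look shifted by one column. Nothing below uses those columns to establish the week-16 mark.

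**2. Size of the gap.**
- Week 14 = 14 × 7 = day 98; week 16 = 16 × 7 = day 112; gap = 112 − 98 = 14 days.
- With the calendar window of ±2 days at week 16, the visit is 12 to 16 days after day 98.
- With the ±7 days that Table 6.1 allows without a deviation, it is 7 to 21 days after day 98.

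**3. Drug remaining.** Section 2.3.1.3 states: "The half-life was 2.3–4 hours".
- 14 days = 14 × 24 = 336 hours.
- 336 / 4 = 84 half-lives; 336 / 2.3 = 146 half-lives.
- At the earliest permitted visit: 7 × 24 = 168 hours, and 168 / 4 = 42 half-lives.

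The drug is cleared at every permitted visit date under the day-98 reading, and present under the calendar reading.

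**4. Planned exposure.** (112 − 98) / 98 = 14.3% more days under the calendar than under the text.

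**5. Do the follow-up visits settle the stop day?** Section 11 schedules scans "at weeks 8, 16, 26 and every 3 months through 1 year according to standard practice", and Table 6.1 has a week-26 visit. The calendar has 10-week and 36-week post-treatment visits.
- Counted from week 16: 16 + 10 = 26 and 16 + 36 = 52.
- Counted from week 14: 14 + 10 = 24 and 14 + 36 = 50.

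The week-16 sums fit better. But the 10-week visit and the Table 6.1 visit each allow ±14 days, and 24 + 2 = 26. The starting point of the post-treatment count is not defined. This is weak corroboration and does not settle the question.

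**6. What is and is not affected.** Section 5.1 compares pretreatment with day 21, and day 21 with day 42. Both comparisons end before day 98.

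**The case against.** The strongest reply is that the calendar row runs into an arrow towards repeat cycles, so the week-16 mark may stand for patients continuing on drug. Sections 5.1 and 5.4 do allow continuation, and such patients could properly be on drug at week 16. This limits the conflict to patients who receive cycle 1 only. It does not remove it, because the mark carries no such restriction and continuing patients have their own column.

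Second, the stakes are secondary. The biopsy is optional. Sections 2.4.4, 9.2.3 and 9.2.6 make week-16 blood optional too, Section 9.2.4 asks for it if possible, and the calendar footnotes the T-cell subset draw as optional. Table 5.1 and Section 11 list the draw without that qualifier. This stands as a limit on the size of the problem.

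Third, doses are recorded in the medication diary, so on- or off-drug status can be recovered. That stands as well. It makes the remedy cheap, but the plan does not call for using the diary in this way.

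A reader might also infer more than the documents support:
- **That the follow-up visits prove treatment ends at week 16.** The visit windows and the undefined starting point leave both readings open.
- **That the 30-day safety reporting window becomes ambiguous.** Section 7.3.3 counts it from the last administration, so it follows the actual last dose.
- **That sites have dosed differently.** Nothing documents this; it is only a risk.
- **That week-16 Kyn/Trp values are affected.** Section 9.2.5 ties this assay to biopsy times, but the extracted calendar does not place a mark at week 16, so it is not counted here.

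**Conclusion.** The contradiction holds. The Schema and Table 5.1 (98 days, Cohorts A and B), the Cohort B sentence in Section 5.1 and the three-month course for all patients conflict with a calendar that marks dosing through day 112. The protocol equates 98 days with three months, so the general sentence sides with the tables; for patients outside Cohorts A and B it is the only statement of duration in the treatment text.

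For patients receiving cycle 1 only, week-16 samples are on drug under one reading and about 14 days off drug, with the drug cleared, under the other. Planned exposure differs by 14 days. It is tempting to extend this to the primary endpoint, but comparisons at days 0, 21 and 42 cannot be affected by a stop day of 98 or later.

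The conclusion rests on the calendar alignment up to week 16, which two independent rows confirm, and on the half-life quoted in the protocol. The documents do not show which last day is intended, and this review takes no position on it. The point should be corrected, but it does not threaten the main result.

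**What to change.** 1. Reconcile the last day of cycle-1 INCB024360 across the Schema (including the row for all other patients), Section 5.1, Table 5.1, Section 5.4 and the Study Calendar. If the week-16 mark is meant only for patients continuing to further cycles, add a footnote saying so.
2. State the day from which the 10-week and 36-week post-treatment visits are counted.
3. In Sections 9.2 and 11, derive an on/off-drug flag for each week-16 sample from the last-dose date in the medication diary, covering patients who continue to further cycles. Show week-16 immune results by that flag.

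The cost is a wording change in a few places, one calendar correction or footnote, and one derived variable from data already collected. No patients, visits or assays are added.

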3.1.3 Prior and concurrent therapy

- 3.1.3.1 Patients may have had prior systemic therapy without constraint on the number of prior treatment regimens except:
- a) Patients may not have had $>450 \text{ mg/m}^2$ doxorubicin
 - b) Patients may not have had $>3000 \text{ cGy}$ to fields encompassing the entire pelvis
- 3.1.3.2 Patients must not be on any other systemic therapy within the following intervals before study enrollment:
- a) 1 week after stereotactic radiosurgery of the brain or comparable technology
 - b) 4 weeks after cytotoxic chemotherapy or external beam radiation therapy
 - c) 6 weeks after chemotherapy regimens including BCNU (carmustine) or mitomycin C
 - d) patients who experience melanoma progression (by RECIST 1.1 criteria) while on or after treatment with PD-1 or PDL-1 antibody may enroll on this study.

NOTE: Patients must be off PD-1/PDL-1 antibody for at least 2 weeks to assess for delayed toxicity before being enrolled and receiving INCB024360. Patients who are enrolled 2 weeks and up to 6 weeks after the last dose of PD-1/PDL-1 antibody will enroll in cohort B and receive 100mg BID of INCB024360.

Patients enrolled beyond the 6 week period after failing anti-PD-1/PDL-1 will be enrolled in cohort A. Cohort A patients will receive 300mg BID of INCB024360.

Patients must not have active grade 2 autoimmune toxicities attributed to these antibodies at study entry.

- e) 8 weeks after ipilimumab, other CTLA-4 antibody or other immunologically active antibody.

NOTE: Patients receiving prior CTLA-4, anti-PD1 antibody or other immunologic therapy must show evidence of normal pituitary function at baseline and must not have active grade 2 autoimmune toxicities attributed to these antibodies at study entry.

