5.1.1 CTEP IND Agent(s): N/A

5.1.2 Other Agent(s): **INCB024360**

Combining INCB024360 with the multipeptide vaccine MELITAC 12.1 is a novel approach. Although no adverse findings in toxicology or safety pharmacology assessments have been described herein, and the most common grade 1 or 2 AEs at the recommended Phase-II dose (600 mg) include fatigue, nausea and vomiting, constipation, and anorexia; to decrease the possibility of unanticipated toxicities with the combination, the dose of INCB024360 in the first 3 patients treated in the study will be at the dose of 300 mg bid.

Weak cross-reactivity of INCB024360 to the human vasopressin 1a receptor, dopamine receptor, and carbonic anhydrase II may lead to changes in blood pressure or blood electrolytes. In 28-day toxicology studies, C_{max} values have exceeded the IC_{50} for the IDO1 enzyme (72 nM) by up to 37-fold and the IC_{50} for the vasopressin 1a receptor by up to 4-fold (13-fold in single-dose studies) in the absence of any toxicity, so the risk of unintended pharmacological activity is expected to be low.

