12.3 Collaborative Agreements Language – N/A

13. STATISTICAL CONSIDERATIONS

13.1 Study Design/Endpoints

The proposed study is a Phase II, open label, multicenter study of the administration of INCB024360, an IDO1 inhibitor, plus a multipeptide melanoma vaccine, MELITAC 12.1, in patients with advanced (i.e., surgically incurable stage III or IV) melanoma having tissue amenable to serial biopsy.

The first 3 patients will be administered the INCB024360 in a reduced amount of 300 mg bid and enrolled in a staggered design with a 2-week waiting period between each of the first 3 patients ([Table 5.1](#)). This is a safety precaution due to unknown effects of the combination of INCB024360 with the multipeptide melanoma vaccine. Although both agents have excellent safety profiles, unexpected toxicities could occur when used together.

Each patient's tumor(s) will be biopsied before therapy and during therapy to assess the effects of INCB024360 and vaccine by IHC and transcriptome analysis ([Table 5.1](#)).

INCB024360 is expected to normalize serum Kyn/Trp ratios, in turn altering the tumor microenvironment, which includes the number and character of tumor-infiltrating T cells. The addition of MELITAC 12.1, a multipeptide melanoma vaccine, will be used to compare INCB024360 alone and with the vaccine. Effects of IDO inhibition on systemic vaccine-induced immunity will be assessed by evaluating peripheral blood immune responses to the MELITAC 12.1 vaccine. The comparator for immune responses will be taken from published experience with similar patients treated with the same vaccine regimen but without INCB024360 [[[name] 2011](#); [[name] 2009](#)].

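### A DLT in the safety lead-in triggers no defined dose change, and the lead-in dose rule contradicts the Cohort B dose rule

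*Combined protocol and SAP*

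**What the plan says.** **Lead-in.** Section 5.1 sets the starting dose by order of enrollment: "the first 3 patients enrolled in the study will be at the dose of 300 mg bid". Section 5.1.2 repeats this for the first three patients treated, and Section 13.1 repeats it again. Starts are staggered, and enrollment halts once three patients are in.

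**After the lead-in.** Section 5.1 continues, with a pointer to Table 5.1: "The next nine patients will receive either 300 mg bid of INCB024360 or 100 mg bid". The next sentence is presented as a safety measure. It says that if a DLT occurs in the first three patients treated at 300 mg, "the subsequent 9 patients will be treated with the dose of either 300 mg BID or 100 mg of INCB024360 + MELITAC 12.1". The text after Table 5.1 adds that once the first three are "found to tolerate the combination well, the dose of INCB024360 will be 300 mg BID for subsequent patients". It then assigns 300 mg bid to Cohort A, 100 mg bid to Cohort B and 300 mg bid to all others.

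**Stopping.** Section 5.1 stops the study at two DLTs in the first six patients treated at 300 mg. Section 6 closes accrual if more than 33% of accrued patients have a treatment-related DLT, but accepts one such DLT among the first three.

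**Cohort B.** Under Section 3.1.3.2, patients enrolled 2 to 6 weeks after their last PD-1/PD-L1 antibody dose "will enroll in cohort B and receive 100mg BID". The Schema and Section 5.1 agree. None of these places closes Cohort B while the lead-in is running.

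**The concern.** The staggered start and the halt exist to inform what happens next to patients on a combination that Section 5.1.2 describes as novel. A rule headed as a safety measure should say what a DLT changes. This one lists the two doses already available and names no patients, criterion or decision-maker. After one lead-in DLT, a site could read it as assignment by cohort, as usual, or as permission to give 100 mg to patients who would otherwise get 300 mg.

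The choice also affects safety monitoring. The Section 5.1 stopping rule counts only patients treated at 300 mg, so the unstated dose decision determines how many later patients enter that count.

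The second problem is a direct contradiction. An early enrollee who is, say, 3 weeks past the last antibody dose is assigned 300 mg by the lead-in rule and 100 mg by the Cohort B rule.

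**Working it through.** **1. Enrollment arithmetic.** 3 lead-in + 9 subsequent = 12, which matches the total in Section 5.1. The nine are 9/12 = 75% of patients.

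**2. Doses for the nine, by situation.**

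| Situation | Place | Doses named | Who gets which |
|---|---|---|---|
| No condition stated | 5.1, before Table 5.1 | 300 or 100 mg bid | By cohort, through Table 5.1 |
| DLT in first three | 5.1, next sentence | 300 mg bid or 100 mg (no frequency) | Not stated |
| Lead-in tolerated | 5.1, after Table 5.1 | 300 mg bid; 100 mg bid for Cohort B | By cohort |
| Lead-in not tolerated | 5.1, after Table 5.1 | None | Not stated |

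Section 6 does not fill the empty cells. Its acceptance of one treatment-related DLT in three settles whether accrual continues, not the dose. Its management tables offer continuing without change or coming off therapy, sometimes with a condition attached. They contain no dose-reduction step, although Section 5.1 refers to Section 6 for dose modifications.

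**3. How often the gap would be reached.** The documents give no expected DLT rate, so p is an assumption. Exactly one DLT in three, which Section 6 accepts, has probability 3p(1−p)². After that, one more DLT in the next three patients at 300 mg meets the Section 5.1 stop, with probability 1−(1−p)³.

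| Assumed p | Exactly 1 of 3 | At least 1 in the next 3 at 300 mg | At least 2 of 6 |
|---|---|---|---|
| 10% | 0.243 | 0.271 | 0.114 |
| 20% | 0.384 | 0.488 | 0.345 |
| 33% | 0.444 | 0.699 | 0.642 |
| 50% | 0.375 | 0.875 | 0.891 |

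For example, at 20%: 3 × 0.2 × 0.8² = 0.384, and 1 − 0.8³ = 0.488. The last column is 1 − (1−p)⁶ − 6p(1−p)⁵, the chance of the Section 5.1 stop if six patients are treated at 300 mg.

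**4. Lead-in against Cohort B.** Let q be the share of enrollees who meet the Cohort B definition, also an assumption. The chance that at least one of the first three falls under both dose rules is 1−(1−q)³:

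- q = 10%: 0.271
- q = 20%: 0.488
- q = 30%: 0.657
- q = 50%: 0.875

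**5. The two counts.** Section 5.1 ties the halt to three patients enrolled, but the DLT rule to three patients treated at 300 mg. If one of the first three receives 100 mg, the halt comes with two patients at 300 mg. The third patient at 300 mg is then number four or later. With a total of 12 and no replacements, at most 12 − 4 = 8 patients remain, not the nine in the DLT sentence.

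**The case against.** **The two dose sentences need not mean the same thing.** The first cites Table 5.1, where dose follows cohort; the second does not. It can be read as opening 100 mg to patients who would otherwise get 300 mg. This stands as a possible reading, so the branches are not proven identical. It still leaves open which patients, on what criterion and by whose decision.

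**The lead-in is not idle.** A reader might infer that it cannot affect any dose or has no effect. The documents do not support that. The staggered start, the halt and both stopping rules remain, and Section 6 sends related toxicities to the investigators, CTEP and the coordinating center to consider a schedule change. What is missing is a pre-specified dose consequence.

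**Free choice for nine patients.** A reader might also infer that dosing of all nine is left to sites. Without a lead-in DLT, Table 5.1 and the cohort definitions fix the dose by time since antibody. The ambiguity is confined to the DLT case.

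**The word reduced in Section 13.1.** That section says "The first 3 patients will be administered the INCB024360 in a reduced amount of 300 mg bid", and a reader might infer an error because no one in this trial gets more. Sections 2.3.1.3 and 5.1.2 supply the reference, a recommended monotherapy dose of 600 mg bid, so this is not a defect.

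**The counting and the missing frequency.** The DLT rule and the text after Table 5.1 already refer to patients at 300 mg; only the halt is tied to enrollment. Table 5.1 gives the twice-daily frequency that the DLT sentence omits. Both observations are fair, and both items are minor.

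**Cohort B was a later addition.** Section 2.4.3 says so, and the wording about the next nine may hint that 100 mg was meant only after the lead-in. If the lead-in had finished first, the collision would not arise in practice. The current text says neither, and still states the lead-in prospectively.

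**Conclusion.** The point holds in two parts, and both rest on the text alone. First, a DLT in the first three patients has no defined dose consequence for the nine who follow (75% of enrollment). Second, the lead-in and Cohort B rules assign different doses to the same patient with no order of precedence, and the halt could come with fewer than three patients at 300 mg.

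The probabilities show only that neither situation is remote. Exactly one DLT in three has probability 0.24 to 0.44 for assumed DLT rates between 10% and 50%. A dose conflict among the first three has probability 0.27 to 0.88 if 10% to 50% of enrollees meet the Cohort B definition. The documents support no particular value for either rate. Nothing here says which dose or rule is right.

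**What to change.** Reconcile the Schema and Sections 3.1.3.2, 5.1 (before and after Table 5.1), 5.1.2, 6 and 13.1 in one amendment:

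- **DLT sentence in 5.1.** Either state what differs from the no-DLT case, for which patients and who decides, or remove it as having no dose consequence. If it stays, give the frequency for the 100 mg dose.
- **Text after Table 5.1.** Say what follows if the first three do not tolerate the combination, consistently with Section 6.
- **Precedence.** State which rule governs a patient who meets both the lead-in and the Cohort B definitions.
- **Count.** Use the same count for the halt and the DLT rule, and adjust the number of subsequent patients to match.

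The sponsor's clinical team decides the doses and rules. The cost is a short amendment and possibly a brief wait for an early candidate; the sample size and assessments do not change.
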